6.6 Double-Blind, Placebo-Controlled Food Challenge (DBPCFC)

The DBPCFC is to be conducted as 2 challenges, each part on a separate day, using a placebo (artificially peanut-flavored oat flour) for 1 challenge and peanut (as defatted peanut flour) for the other. The 2 challenge days should be scheduled as closely together as practicable (allowing the washout period for antihistamines) and should not be scheduled more than 7 days apart. The oral food challenge is to be performed under double-blind conditions so that neither the subject, nor the subject's caregiver, nor any of the clinic staff (except the unblinded preparer of the challenge foods) knows which challenge contains the peanut or the placebo. The same vehicle food should be used for both parts of the DBPCFC. The clinic staff may not be unblinded as to the order of the 2 parts (peanut and placebo) of the DBPCFC until after completion of the observation period of the second part of the challenge.

The DBPCFC will consist of administering gradually increasing challenge doses of a peanut flour mixture (containing approximately 50% peanut protein) or a placebo (oat) flour mixture, mixed in a vehicle food, at 20 to 30 minute intervals. The placebo flour mixture will be supplied pre-mixed with a small amount of artificial peanut flavor to provide a reasonable

degree of taste-matching of the final placebo/vehicle food mixture to the peanut/vehicle food mixture. Additional, non-allergenic, powdered flavoring agents have been added both to the peanut and placebo flour mixtures to help further mask the distinctive flavor of peanut. A small amount of oat flour has been added to the peanut flour mixture to help match its consistency to the placebo flour mixture. Investigational sites will be provided with standardized recipes for preparation of the DBPCFC in a separate manual of procedures.

Prior to performing DBPCFC, the subject must be:

- Clear of antihistamines and other medications that could interfere with the assessment of the DBPCFC, for an appropriate length of time (5 half-lives of the antihistamine or other medications in question).
- Assessed for an exacerbation of asthma (if asthmatic) as determined by active wheezing or a PEFR < 80% of predicted.
- Free from active wheezing, a flare of atopic disease (eg, atopic dermatitis), or suspected intercurrent illness prior to DBPCFC.
- Fully recovered (ie, back to their baseline state of health) from any preceding illness for at least 3 to 7 days, depending on the investigator-determined severity of the illness. Subjects should be maintained on their current, or a reduced, dose level of IP until their flare of asthma, atopic disease, or intercurrent illness has resolved.

Oral food challenges will be undertaken under direct medical supervision and with emergency medications and trained staff immediately available. The DBPCFC is performed by feeding gradually increasing amounts of a suspect allergenic food (in this case, peanut, presented as defatted peanut flour) mixed in a vehicle (matrix) food under physician observation ([Bock and Atkins, 1990](#); [Burks et al, 2012](#)). For this study, a uniform approach to food challenge in accordance with the PRACTALL consensus guidelines for DBPCFC will be used by all investigational sites. According to the PRACTALL guidelines, the challenge doses start at 1 mg and increase in semi-log increments to a maximum dose of 3000 mg. The DBPCFC dose escalation schedules used in the current study have been modified slightly from the PRACTALL recommendations, and are presented in [Table 3](#).

Table 3 Modified PRACTALL DBPCFC Doses Using Peanut Flour with 50% Peanut Protein Content for Screening and Exit DBPCFC

Challenge Doses				
Amount of Peanut Protein at Each Challenge Dose (mg)	Amount of Peanut Flour with 50% Protein Content (mg)	Cumulative Amount of Peanut Protein (mg) at Screening	Cumulative Amount of Peanut Protein (mg) at Exit	
Screening only	1	2	1	0 (or 1) ^a
Screening and Exit	3	6	4	3 (or 4)
Screening and Exit	10	20	14	13 (or 14)
Screening and Exit	30	60	44	43 (or 44)
Screening and Exit	100	200	144	143 (or 144)
Screening and Exit	300	600	444	443 (or 444)
Exit only	600	1200	-	1043 (or 1044)
Exit only	1000	2000	-	2043 (or 2044)

^a For explanation of contingent/optional doses indicated in parentheses refer to [Section 6.6.2](#).

For each subject, a Blinded Evaluating Physician (Blinded Assessor) is to be designated to assess the tolerability of the challenge doses presented in the DBPCFC. The Blinded Assessor, who is assessing and managing subject AEs on the food challenge days, is not to be involved directly in the oversight of study product dosing or the assessment or management of AEs during the initial escalation, up-dosing, or maintenance phases of the study; nor should they be involved in the preparation of the food challenge material preparation on the food challenge days (for details refer to the Masking Plan). To the extent practicable, the same Blinded Assessor who determines DLS in the Screening DBPCFC should determine DLS in the Exit DBPCFC.

Vital signs (BP, pulse rate, and body temperature) are to be measured just prior to each challenge dose of the DBPCFC or at 15 to 20 minute intervals post-dose, if the between challenge-dosing interval is prolonged. Assessment for signs and symptoms of allergic reaction is to be performed at the time that vital signs are checked.

Each part of the DBPCFC is halted when the investigator determines that DLS have occurred. Dose-limiting symptoms, in the setting of the DBPCFC, are any symptoms that, in the investigator's assessment, indicate poor tolerability of the last challenge dose administered, and preclude safe advancement to the next challenge dose.

Dose-limiting symptoms, typically objective symptoms (signs), indicate a positive reaction and termination of dosing. The criteria for determining if symptoms are dose limiting during DBPCFC are the same as for determining whether a specific dose during up-dosing is tolerated ([Section 6.7](#)) with the exception that even mild symptoms, if they require pharmacological treatment, will be considered dose limiting.

For clarity, a tolerated dose in the context of the DBPCFCs, is defined as a dose that is successfully consumed with no more than mild symptoms, not requiring any pharmacological treatment, which are consistent with the following criteria:

- Isolated to a single organ system
- Do not require administration of epinephrine
- Are not worsening in intensity or distribution over time
- Resolve, or shows definite signs of resolving, in under 1 hour. Do not include objective wheezing.

As with up-dosing, severe symptoms will always be assessed as dose limiting; and moderate symptoms, with only rare exceptions (requiring a documented explanation), will also be assessed as dose limiting. Mild symptoms, on the other hand, may or may not be assessed as dose-limiting ([Section 6.7](#)).

In general, if an investigator is unwilling to advance to the next challenge dose in a DBPCFC because of the emergence of allergic symptoms, the last symptom-eliciting challenge dose should be considered to have been not tolerated due to DLS. However, exceptions to this may occur, as for example if an emotional reaction to continuing the challenge dose escalation interferes with the ability to progress the dose escalation to the point where convincingly (typically objective) DLS occur. Any such instances must be accompanied by an explanation in the CRF.

On the days that subjects undergo DBPCFCs (Screening and Exit), they must, at a minimum, be observed for 2 hours after administration of the last challenge dose, with vital sign measurements and assessment for signs and symptoms of allergic reaction performed every 30 minutes. Any signs or symptoms of allergic reaction will be recorded in the CRF on the appropriate Dosing Symptom/AE form.

If DBPCFC is completed with no symptoms detected after 2 hours of observation following the last challenge dose, the subject may be sent home from the CRC. If the subject exhibited mild symptoms, the duration of the observation period should be extended to a minimum of 1 hour after resolution of the symptoms. For moderate symptoms, the observation period should be extended to a minimum of 2 hours after resolution of the symptoms. And for severe symptoms, the subject should be observed for a minimum of 3 hours after resolution of the symptoms, either at the CRC or an emergency facility, as appropriate.

On the day following DBPCFC, the site is to make telephone contact with the subject or subject's parent or guardian to enquire if any AEs (including allergic symptoms) occurred subsequent to the subject leaving the clinic, and to provide assistance in the recording of any such events.

6.6.1 Screening Double-Blind, Placebo-Controlled Food Challenge (DBPCFC)

The initial (Screening) DBPCFC for eligibility will consist of administering gradually increasing challenge doses of a peanut flour mixture (containing approximately 50% peanut protein) or a placebo (oat) flour mixture, mixed in a vehicle food, at 20 to 30 minute intervals. The placebo flour mixture will be supplied pre-mixed with a small amount of artificial peanut flavor to provide a reasonable degree of taste-matching of the final placebo/vehicle food mixture to the peanut/vehicle food mixture. Additional, non-allergenic,

powdered flavoring agents have been added both to the peanut and placebo flour mixtures to help further mask the distinctive flavor of peanut. A small amount of oat flour has been added to the peanut flour mixture to help match its consistency to the placebo flour mixture. Investigational sites will be provided with standardized recipes for preparation of the DBPCFC in a separate manual of procedures.

The Screening DBPCFC will be performed in accordance with PRACTALL guidelines, but requiring progression in a fixed sequence without repeating any dose. The procedure will also be modified in that the highest dose will be capped at 300 mg (444 mg cumulative) peanut protein or placebo, as shown in [Table 3](#). Otherwise, the PRACTALL recommendations for maintaining safety and assessing symptom severity serve as useful guidelines.

The DBPCFC is to be conducted as 2 challenges, each part on a separate day, using a placebo (artificially peanut-flavored oat flour) for one challenge and peanut (as defatted peanut flour) for the other. The 2 challenge days should be scheduled as closely together as practicable and should not be scheduled more than 7 days apart. The oral food challenge is to be performed under double-blind conditions so that neither the subject, nor the subject's caregiver, nor any of the clinic staff (save for the unblinded preparer of the challenge foods) knows which challenge contains the peanut or the placebo. The same vehicle food should be used for both parts of the DBPCFC. The clinic staff may not be unblinded as to the order of the 2 parts (peanut and placebo) of the DBPCFC until after completion of the observation period of the second part of the challenge.

6.6.2 Exit Double-Blind, Placebo-Controlled Food Challenge (DBPCFC)

The Exit DBPCFC will be conducted in a manner similar to the Screening DBPCFC, but starting at a dose of 3 mg of peanut protein (except for subjects who failed their Screening DBPCFC at 1 mg), and with the last 3 challenge doses progressing from 300 mg (443 mg cumulative) to 600 mg (1043 mg cumulative) and then to 1000 mg (2043 mg cumulative) of peanut protein as shown in [Table 3](#).

The same vehicle food should be used for the Exit DBPCFC as was used for the Screening DBPCFC.

Dosing with food challenge materials should continue on the days between the 2 parts of the Exit DBPCFC, according to the same dosing guidelines that apply throughout the Maintenance Period.

Subjects who failed their Screening DBPCFC at the 1 mg challenge dose of peanut protein will be required to start the Exit DBPCFC with a 1 mg dose. At the investigator's discretion, a 1 mg dose may be added at the beginning of the escalation (for a maximum cumulative dose of 2044 mg peanut protein) of any subject's Exit DBPCFC.

Subjects will be considered desensitization responders for the primary endpoint analysis if they are able to tolerate an Exit DBPCFC challenge dose of 1000 mg (2043 mg cumulative) of peanut protein with no, or only mild, symptoms.

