3.2 Treatment Phase

The Treatment Phase comprises 3 periods:

- **Initial Escalation** (2 consecutive days) – Eligible subjects will be randomized and initiate OIT starting at a dose of 0.5 mg of IP, and then increase the dose incrementally at 20 to 30 minute intervals over the course of a single day to a maximum dose of 6 mg. Subjects who fail to tolerate at least a 3 mg dose will be considered escalation failures and will be discontinued from the study. Subjects who tolerate both the 3 mg and 6 mg doses of IP, or who tolerate the 3 mg but not the 6 mg dose, will undergo confirmatory testing of the tolerability of a 3 mg dose the following consecutive day (refer to Initial Escalation Schedule at end of synopsis). Subjects who tolerate this confirmatory dose will enter the Up-dosing Period. Subjects who do not tolerate this confirmatory dose will be discontinued. Therapy details are found in [Section 3](#) and [Section 6](#) of the protocol.

- **Up-dosing Period** – After the initial escalation period, subjects will report to the CRC every 2 weeks to escalate their OIT dose to an expected daily dose of 300 mg of peanut protein. This constitutes the Up-dosing Period. Subjects will receive daily oral dosing of peanut or placebo OIT for approximately 20 weeks, if up-dosing proceeds without holding at, or reducing, a dose level; up to 40 weeks, maximum. All escalation doses will be administered in a CRC or other monitored setting (unless required by a specific institution, no distinction will be drawn between an investigational site, study center office, clinic, or CRC, provided the capability requirements for monitoring and emergency intervention are met by the facility). All up-dosing activities will be performed under direct observation. Therapy details are found in [Section 3](#) and [Section 6](#) of the protocol.
- **Maintenance Period** – Those subjects who reach the target maintenance dose of 300 mg/d of IP will enter an approximately 12-week Maintenance Period of continued dosing at 300 mg/d, which may be extended by up to an additional 4 weeks (for a maximum Maintenance Period duration of 16 weeks), or to a total Treatment Phase duration of 56 weeks, whichever occurs first.

Treatment will be conducted in a double-blind fashion. The IP (AR101 or placebo) will be coded according to subject randomization number. The subjects and the investigational site personnel will be blinded to treatment assignment.

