5.2 Preparation, Administration, and Dosage

The first dose at each new dose level is to be administered in the CRC with the oversight of a physician. This dose, intended for in-clinic administration, is removed from the dosing kit for the assigned dose level. Once a dose is removed from a dosing kit, the kit must be dispensed to the subject or held at the site for documented destruction or return to the sponsor's designee (as instructed); once opened, dosing kits cannot be used for any other dosing interval or any other subject. At each clinic visit, subjects will receive a kit of capsules or sachets to be taken at home according to their specific dose level. The subjects will be instructed to document capsules and sachets taken at home using diary logs and to bring all unused capsules and sachets back to the clinic at the next visit. The subjects will be instructed to store the dosing kit in the refrigerator other than when it is removed to obtain the daily dose.

In exceptional circumstances when a subject is unable to return to the CRC for the next scheduled visit (eg, travel, holidays) and continued dosing is necessary, an additional dosing kit may be dispensed on a case-by-case basis after submission of a documented request and medical monitor approval. One additional dosing kit may be dispensed to continue the current dose level if there are no safety concerns in the opinion of the investigator and medical monitor (eg, the dose level is tolerated, no intercurrent illnesses) and the subject will have access to appropriate emergency medical services as needed. Up-dosing is not allowed until the next clinic visit.

Procedures for preparation and administration of doses given in clinic or at home are the same. Dose preparation is to be completed by the subject or supervising adult, as age-appropriate. (For in-clinic dosing, dose preparation may be performed by clinic staff or by parent/subject under the direct supervision of clinic staff for the purpose of teaching and reinforcing training.) The capsules should be pulled apart, and gently rolled between finger and thumb, followed by a light tap to the end of each half of the capsule to ensure full

delivery of contents. The contents of the capsules or the sachets are to be mixed with a vehicle food, such as apple sauce, yogurt, pudding, or other palatable, age-appropriate food. Care must be taken not to inhale the powder as this could provoke worsening of asthma or induce an allergic reaction.

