6.3 Study Treatment Visits

6.3.1 Confirmation of Eligibility and Randomization

At the end of the Screening DBPCFC assessment, the food challenge materials will be unblinded to establish whether any DLS demonstrated by the subject were a result of the peanut or the placebo food challenge material. If DLS are established to have occurred as a result of (only) the peanut food challenge material the following steps will be taken:

- Assessment that the subject still meets all eligibility criteria – a Subject Eligibility Form, which documents subject eligibility, is completed and sent to the medical monitor for review
- Medical monitor will review the Eligibility Form and confirm whether the subject is eligible to proceed to randomization (within 72 hours of receipt of the completed Eligibility Form), if applicable.
- Subject's Initial Escalation Day 1 visit is confirmed and should occur such that Initial Escalation Day 1 is not later than 29 days following the signing of the consent/assent form. Any deviation from this window must be discussed with and agreed by the medical monitor.
- Before randomization, inclusion and exclusion criteria are reviewed again to confirm the subject remains eligible for the study.

- The randomization day and Initial Escalation Day 1 should ideally be the same date. The investigator, or designee, will randomize the subject in the interactive response system on Initial Escalation Day 1 prior to the first dose of IP. The exception to this is if it is not logistically feasible to randomize a subject and commence initial escalation dosing on the same day; in this situation the site may randomize a subject in the interactive response system shortly (maximum 3 days) prior to Initial Escalation Day 1.

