6.3.4 Maintenance Period

The first Maintenance Visit will occur 2 weeks after the start of dosing at 300 mg/d; thereafter, Maintenance Visits will occur approximately every 4 weeks.

Subjects should withhold their daily home dose of IP on in-clinic dosing days, but should take all other prescribed medications as scheduled.

The following assessments/procedures are scheduled for each in-clinic dosing Maintenance Visit in the CRC:

- Concomitant medication review
- Contraception review
- Diet (food allergen exposure) history update
- Return unused IP to the clinic at each visit
- Symptom-directed physical examination
- Pre-dose vital sign measurement (BP, pulse rate, body temperature)
- PEFR (3 attempts are to be performed, and the best value taken). PEFR should be measured at the same time of day for each visit assessment (eg, morning, afternoon, evening).
- IP administration under observation in the clinic
- Post-dose vital sign measurements (BP, pulse rate) at the following times:
 - Within 15 to 30 minutes post-dose;
 - At 30 minute intervals thereafter, and for the duration of the post-dose observation period is extended beyond 30 minutes.
- Provide subject with take home sachets (or capsules, as appropriate) for daily dosing until next visit
- Monitoring for dosing compliance
- Monitoring for AEs, including allergic symptoms (below and [Section 6.7](#) and [Section 7.2](#))
- Review home dosing instructions (only at first visit in Maintenance Period)

- Subjects will be reminded to continue to follow a peanut-avoidant diet for the duration of the study.

In the event that dose reduction from the stable dose of 300 mg/d is required during the last weeks of the planned 12-week Maintenance Period, the Maintenance Period may be extended on an individual basis up to an additional 4 weeks (to a maximum of 16 weeks) or to a maximum study duration of 56 weeks, whichever is shorter. The Exit DBPCFC must be performed by Study Week 56. Additionally, subjects must maintain a dose of 300 mg/d for at least the last 4 consecutive weeks of the Maintenance Period without the use of symptomatic therapy to qualify for the Exit DBPCFC. Failure to do so will result in the subject being discontinued from the study.

If dosing is discontinued, the subject will be asked to return to the CRC 14 to 16 days following his or her last dose of AR101 to undergo an Early Discontinuation Visit ([Section 6.4](#)).

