6.7.7 Reactions Occurring During the Maintenance Period

This phase consists of the subject receiving the 300 mg/d dose of IP for approximately 12 weeks. For any noted symptoms during the Maintenance Period, the same IP dosing guidelines and procedures will be followed as for the Up-dosing Period.

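### Section 6.6.2 names the wrong product for dosing between the two parts of the Exit DBPCFC: it says food challenge materials where the rules it invokes cover only IP (minor drafting error)

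*Protocol*

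**What the plan says.** The sentence at issue is in Protocol Section 6.6.2, on the conduct of the Exit DBPCFC: "Dosing with food challenge materials should continue on the days between the 2 parts of the Exit DBPCFC", to be done "according to the same dosing guidelines that apply throughout the Maintenance Period".

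The Maintenance Period is described elsewhere as a period of dosing with IP:

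- Section 3.2: subjects who reach the "target maintenance dose of 300 mg/d of IP will enter an approximately 12-week Maintenance Period of continued dosing at 300 mg/d".
- Section 6.3.4, on what is handed out at Maintenance Visits: "Provide subject with take home sachets (or capsules, as appropriate) for daily dosing until next visit". The same section has IP given under observation in the clinic.
- Section 6.7.7: "For any noted symptoms during the Maintenance Period, the same IP dosing guidelines and procedures will be followed as for the Up-dosing Period".

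The challenge foods are described separately. Section 6.6 has each DBPCFC run as two challenges on separate days, "using a placebo (artificially peanut-flavored oat flour) for 1 challenge and peanut (as defatted peanut flour) for the other". Section 6.3.1 uses the same term as the disputed sentence when the Screening challenge is unblinded to learn whether dose-limiting symptoms "were a result of the peanut or the placebo food challenge material".

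**The concern.** The noun and the rule in the sentence belong to different products. A site following the noun would give peanut flour or oat flour on days when no challenge is under way. A site following the rule would give IP.

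The literal reading is unsafe in principle. Section 3.6 warns subjects against any peanut other than the IP. Section 4.1 admits only children with dose-limiting symptoms at or below 300 mg of peanut protein. Under 3:1 randomization, about 40 of the planned 160 subjects receive placebo and so have had no desensitization before the Exit challenge. Challenge flour given outside the fixed, stepwise, supervised sequence has no place in the design. The error is small, but it sits in the operative text of a safety-sensitive procedure in children.

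**Working it through.** The protocol gives no figure here to reproduce. The check is a comparison of texts, plus a count of the days affected.

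1. **What the invoked rule covers.** Sections 3.2, 6.3.4 and 6.7.7 all speak of IP. None gives a dose, a supply or a schedule for challenge material, so there is no Maintenance dosing with challenge material that could continue. The guidelines are not confined to 300 mg/d: Section 6.3.4 lets dose reduction and re-escalation in Maintenance follow the Up-dosing rules, and Section 6.7.7 does the same for symptoms.

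2. **Whether the term could be another name for IP.** It could not. Food challenge material also appears in the Synopsis (treatment description) and in Sections 3.1, 3.3, 6.3.1 and 6.6, each time for the food given in the DBPCFC. The Synopsis and Sections 3.1 and 3.3 list oversight of study product dosing and preparation of challenge material as separate tasks within one sentence. Section 7.1 states that IP is not used in the DBPCFCs.

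3. **What the rest of the protocol implies for these days.**
   - Section 5.2 requires a dose every day from Day 1, except as needed in treating an adverse event.
   - Section 6.6 keeps subjects with a flare or intercurrent illness on their current or a reduced dose level of IP until it resolves.
   - Section 7.1 considers whether IP taken in the days before the Exit DBPCFC contributed to a reaction.
   - Section 3.6 cautions against peanut other than IP.

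   All of these point to IP. None amends the sentence in Section 6.6.2.

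4. **How many days the sentence governs.** Section 6.6 asks for the two challenge days to be as close together as practicable, allowing for antihistamine washout, and at most 7 days apart. If they are d days apart, the days in between number d − 1.
   - Shortest gap, d = 1 (consecutive days): 1 − 1 = 0 days.
   - Longest gap, d = 7 (for example day 1 and day 8): 7 − 1 = 6 days, namely days 2 to 7.

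   The range is 0 to 6 days per subject. Multiplying these days by 300 mg would count IP doses that subjects are meant to take anyway. It would not measure exposure to the wrong product, so no such figure is given.

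5. **Effect on results.** The document offers no basis for computing an effect on the response rate or on any event rate.

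**The case against.** The strongest reply is that nobody would be misled. The word continue and the reference to the Maintenance Period, both in the sentence itself, identify the product, and the daily-dosing rule in Section 5.2 settles the matter. The literal reading is also hard to carry out. No dose of challenge flour is defined for these days. Section 6.6 has challenge food made by an unblinded preparer and challenges given under direct medical supervision. What families take home is fixed in Section 5.2: "At each clinic visit, subjects will receive a kit of capsules or sachets to be taken at home according to their specific dose level".

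Most of this stands, and it is why the point is minor. It does not make the sentence correct. A reader has to override the stated noun to reach the intended meaning, and the general rules show what was meant without correcting the specific text. Section 6.6 also calls for a telephone contact the day after a challenge, so the sentence is not the only instruction for this interval, but it is the only dosing instruction specific to it.

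A reader might infer more: that IP is to be stopped or replaced between the two parts, so that desensitization lapses and the primary endpoint is biased, or that the blind is put at risk. The document does not support this. The sentence does not direct that IP be withheld, Section 5.2 requires daily dosing, and no route to unblinding can be identified from the text. Nor do two operative rules compete. One noun fails to match the guidelines cited in the same sentence.

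**Conclusion.** The sentence is wrong as written, and the point is minor. Section 6.6.2 names challenge material where the guidelines it cites, and the rest of the protocol, require IP. It applies to 0 to 6 days per subject among those who undergo the Exit DBPCFC. Taken literally it would be unsafe. In practice harm is unlikely, because supply, supervision and the daily-dosing rule all lead to IP. No effect on the primary endpoint, power or error rate is claimed.

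That IP was intended is an inference from the cross-reference and from Sections 5.2, 6.6 and 7.1. The protocol does not say so outright.

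**What to change.** In Section 6.6.2, replace the words food challenge materials with IP (blinded AR101 or placebo) and leave the rest of the sentence unchanged. Do not add 300 mg/d. The existing reference to the Maintenance Period guidelines already supplies the dose and the rules for reducing it, and a fixed dose would conflict with those rules for a child who falls ill or reacts between the two parts. Notify sites of the correction.

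The cost is one noun phrase and one site notification. Design, sample size and analysis do not change.
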